3.4 Safety Endpoints

Safety evaluations include adverse event (AE) monitoring, physical examinations, vital sign measurements, and clinical laboratory testing (hematology and chemistry) as a measure of safety and tolerability for the entire study duration.

3.5 Additional Endpoints

No additional endpoints will be analyzed in the SAP. Pharmacological endpoints will be analyzed separately and is not included in this SAP.

4.0 Analysis Populations

The Full Analysis Set (FAS) includes all randomized subjects who received at least one dose of study drug. The FAS will be used for all efficacy and baseline analyses. Subjects will be included in the analysis according to the treatment groups that they are randomized to.

The Per-Protocol Analysis Set consists of a subset of FAS subjects who did not have any major protocol deviations that are determined to have a potential impact on the primary efficacy endpoint up to Week 24 in Period 1 of the study. Additional analysis of the primary efficacy endpoint will be conducted on the Per-Protocol Analysis Set.

The final criteria and the exclusion of subjects for the per-protocol analysis will be identified prior to the Primary Analysis database lock.

The Safety Analysis Set consists of all subjects who received at least one dose of study drug. Subjects will be included in the analysis according to the study drug that they actually received. The Safety Analysis Set will be used for all safety analysis.

5.0 Subject Disposition

The total number of subjects who were randomized and who were treated will be summarized.

A summary of subject accountability will be provided where the number of subjects in each of the following categories will be summarized for each randomized treatment group:

- Subjects randomized in the study;
- Subjects included in key analysis populations (FAS, Per-Protocol Analysis Set, Safety Analysis Set);
- Subjects who took at least one dose of study drug;
- Subjects who completed Period 1 study participation;
- Subjects who entered Period 2;
- Subjects who completed overall study (Period 1 and Period 2) participation;
- Subjects who prematurely discontinued study drug (all reasons and primary reason).

For end of study participation, the number and percentage of subjects who completed the protocol defined follow-up period (or did not with associated reasons) will be summarized overall and by treatment group.

6.0 Study Drug Duration and Compliance

For the Safety Analysis Set, duration of treatment will be summarized for risankizumab 150 mg and placebo for Period 1, and for risankizumab 150 mg for long-term. Duration of treatment is defined for each subject as last dose date – first dose date + 84 days.

Duration of treatment will be summarized using the number of subjects treated, mean, standard deviation, median, minimum and maximum.

Treatment compliance will be summarized by treatment group at Week 24 for the FAS population. Treatment compliance is defined as the number of injections administered during the subject's participation up to Week 24 divided by the number of injections planned during the subject's participation in the treatment phase up to Week 24.

Compliance will be calculated for each subject and summarized with the mean, median, standard deviation, minimum, and maximum.

7.0 Demographics, Baseline Characteristics, Medical History, and Prior/Concomitant Medications

Demographic, baseline or disease characteristics, medical history, and prior and concomitant medications will be summarized for the FAS by treatment group and overall. Categorical variables will be summarized with the number and percentage of subjects. Continuous variables will be summarized with descriptive statistics (number of non-missing observations, mean and standard deviation, median, minimum and maximum).

7.1 Demographics and Baseline Characteristics

The following demographic and baseline characteristics will be summarized.

Demographic Characteristics

- Sex (male, female)
- Age (years)
- Age Categories (< 65 years, ≥ 65 years, ≥ 65 and < 75 years, ≥ 75 years)
- Race (White, Black or African American, American Indian or Alaska Native, Native Hawaiian or Other Pacific Islander, Asian, Other)
- Geographic Region (North America, South/Central America, Western Europe, Eastern Europe, Asia, Other)
- Ethnicity (Hispanic or Latino, Not Hispanic or Latino)

- Weight (kg)
- Weight Categories (< 100 kg, ≥ 100 kg)
- Height (cm)
- Body Mass Index (BMI) (kg/m²)
- Body Mass Index (BMI) Category (kg/m²) (< 25, ≥ 25 and < 30, ≥ 30)

PsA Medical History and Prior and Concomitant Medications

- Duration of PsA in years
- Duration of PsA in years categories (≤ 5, > 5 and ≤ 10, > 10 years)
- Number of prior csDMARDs (0, 1, 2, ≥ 3)
- Number of prior biologics (0, ≥ 1)
- Number of prior failed biologics (0, 1, ≥ 2)
- Prior exposure to TNF antagonists (yes, no)
- Nonsteroidal anti-inflammatory drug (NSAID) use at Baseline (yes, no)
- Oral Corticosteroid use at Baseline (yes, no)
- Concomitant MTX use at Baseline (yes, no)
- Concomitant csDMARD at Baseline

Any csDMARD

- Any MTX
 - MTX alone
 - MTX and other csDMARD
- csDMARD other than MTX
 - Any sulfasalazine, without MTX
 - Any leflunomide, without MTX
 - Any apremilast, without MTX

None

Baseline Disease Characteristics

Categorical:

- Minimal Disease Activity (MDA) for PsA (yes, no)
- Presence of Dactylitis (LDI > 0) (yes, no)
- Presence of Enthesitis based on LEI (LEI > 0) (yes, no)
- Presence of Enthesitis based on SPARCC (SPARCC Enthesitis Index > 0) (yes, no)
- Body Surface Area (BSA) of psoriatic plaques ($\geq 3\%$, $< 3\%$)
- Presence of spondylitis (yes, no)
- Anti-cyclic citrullinated peptide (Anti-CCP) status (Positive (≥ 17 U/mL), Negative (< 17 U/mL))
- Rheumatoid Factor (RF) status (Positive (≥ 15 IU/mL), Negative (< 15 IU/mL))
- Categories for hsCRP (< 3.0 , ≥ 3.0 mg/L)

Continuous:

- Psoriasis Area and Severity Index (PASI) (for subjects with BSA $\geq 3\%$ at Baseline)
- Disease Activity Score in 28 joints – hsCRP (DAS28(CRP))
- Total dactylitis count (for subjects with presence of dactylitis (LDI > 0))
- LDI (for subjects with presence of dactylitis (LDI > 0))
- Total enthesitis count (for subjects with presence of enthesitis (total enthesitis count > 0))
- LEI (for subjects with LEI > 0)
- Classification Criteria for PsA (CASPAR classification criteria total score)
- BSA of psoriatic plaques (BSA-PsO) (for subjects with BSA $\geq 3\%$ at Baseline and for all subjects)
- SPARCC Enthesitis Index (for subjects with SPARCC Enthesitis Index > 0)
- Tender joint count (TJC68) defined as the number of tender joints out of 68 assessed joints

- Swollen joint count (SJC66) defined as the number of swollen joints out of 66 assessed joints
- Tender joint count (TJC28) defined as the number of tender joints out of 28 assessed joints used for DAS28 calculation
- Swollen joint count (SJC28) defined as the number of swollen joints out of 28 assessed joints used for DAS28 calculation
- Physician's global assessment of disease activity (mm on a 100-mm horizontal visual analogue scale [VAS])
- Patient's assessment of pain (mm on a 100-mm horizontal visual analogue scale (VAS))
- Patient's global assessment of disease activity (mm on a 100-mm horizontal VAS)
- High sensitivity C-reactive protein (hsCRP) (mg/L)
- Health Assessment Questionnaire Disability Index (HAQ - DI) score
- Functional Assessment of Chronic Illness Therapy-Fatigue (FACIT-Fatigue) score
- 36-Item Short Form Health Survey (SF-36) Version 2: physical component summary, mental component summary and the 8 sub-domain scores
- EurQol-5d-5L (EQ-5D-5L) index and VAS score
- Work Productivity and Activity Impairment (WPAI) measures
- Bath Ankylosing Spondylitis Activity Index (BASDAI) score (for subjects with spondylitis at Baseline, for subjects with spondylitis at Baseline confirmed by radiography or MRI)
- Modified BASDAI score (for subjects with spondylitis at Baseline, for subjects with spondylitis at Baseline confirmed by radiography or MRI)
- BASDAI – Spinal Pain (for subjects with spondylitis at Baseline, for subjects with spondylitis at Baseline confirmed by radiography or MRI)
- ASDAS score (for subjects with spondylitis at Baseline, for subjects with spondylitis at Baseline confirmed by radiography or MRI)

Tobacco/Nicotine and Alcohol Use

- Tobacco/Nicotine Use (current, former, never, unknown)
- Alcohol Use (current, former, never, unknown)

7.2 Medical History

Medical history data will be coded using the Medical Dictionary for Regulatory Activities (MedDRA). The actual version of the MedDRA coding dictionary will be noted in the statistical tables and clinical study report. The number and percentage of subjects in each medical history category (by MedDRA system organ class and preferred term) will be summarized overall and by treatment group. The system organ class (SOC) will be presented in alphabetical order, and the preferred terms will be presented in alphabetical order within each SOC. Subjects reporting more than one condition/diagnosis will be counted only once in each row (SOC or preferred term).

7.3 Prior and Concomitant Medications

Prior and concomitant medications will be summarized by generic name. A prior medication is defined as any medication taken prior to the date of the first dose of study drug (risankizumab or placebo). A concomitant medication is defined as any medication that is started prior to the date of the first dose of study drug and continues to be taken after the first dose of study drug or any medication that is started on or after the date of the first dose of study drug and not after the date of the last dose of study drug + 140 days. The number and percentage of subjects taking medications will be summarized by generic drug name based on the World Health Organization (WHO) Drug Dictionary for both prior and concomitant medications. In addition, the number and percentage of subjects taking rescue medication will be summarized by ATC classification level 2, generic drug name and route of administration. A listing of subjects taking rescue medication with generic drug name, dosage and route of administration will also be provided.

8.0 Efficacy Analyses

8.1 General Considerations

All efficacy analyses will be conducted in the FAS Population. In addition, Per-protocol analysis for primary endpoint will be performed. All tests will be 2-sided at an alpha level of 0.05.

The Primary Analysis will be conducted after all ongoing subjects have completed Week 24 and the Week-24 Database Lock has occurred. Efficacy and safety analyses will be performed for Period 1 and long-term efficacy and safety will be summarized through the data cutoff date. An additional interim database lock will be conducted to provide further efficacy and safety exposure for integrated summaries of efficacy and safety supporting the initial regulatory submission; no study-specific analysis will be performed based on this database lock.

Unless otherwise specified, categorical variables will be analyzed using Cochran-Mantel-Haenszel (CMH) test, adjusting for the stratification factors. Continuous variables will be analyzed using Mixed-Effect Model Repeat Measurement (MMRM) method.

Unless otherwise specified, any subject who is randomized based on a wrong stratum will be analyzed according to the actual stratum the subject belongs to.

"Baseline" refers to the last non-missing observation before the first administration of study drug or before randomization if no study drug is given.

Efficacy analysis for Period 1

The efficacy analysis for Period 1 will be performed after all ongoing subjects have completed Period 1 and an interim database lock has occurred. This is the only and final efficacy analysis in Period 1.

Long-term efficacy analysis

Long-term efficacy will be summarized based on data in Period 1 and Period 2 up to data cutoff date for the Week-24 Database Lock. After the initial regulatory submission, additional interim analyses will be performed as deemed appropriate, for example, to address requests from regulatory agencies. The final analysis will be performed after all ongoing subjects complete the study.

The long-term efficacy analysis will be performed on As Observed data (defined in Section 8.2) by randomized treatment group sequence as described below:

1. Placebo → risankizumab 150 mg
2. risankizumab 150 mg → risankizumab 150 mg

There will be no statistical testing for long-term efficacy analysis; only descriptive statistics and 95% confidence intervals will be provided.

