Rationale: *Given the expected size of the subpopulations for these endpoints, the resulting data are not expected to provide adequate power to be clinically meaningful. No data from this study or any other ongoing study was used to make this determination.*

- Section 3.4 – Corrected the description of the endpoint "Change from Baseline in Modified Psoriatic Arthritis Response Criteria (PsARC)" to "Proportion of subjects who achieve a Modified Psoriatic Arthritis Response Criteria (PsARC) response."

Rationale: *Change from baseline is not the correct method to evaluate a binary endpoint.*

- Section 7.3 – Modified wording on the NRI-C and AO imputation methods.

Rationale: *To clarify differences between the NRI-C and AO methods.*

- Section 7.3 – Modified wording on MMRM analysis for continuous variables.

Rationale: *To clarify which data will be used in the MMRM analysis.*

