2.3 Treatment Assignment and Blinding

Subjects will be randomized to risankizumab 150 mg or placebo in a 1:1 ratio.

Randomization will be stratified by current use of csDMARD (0 vs ≥ 1), number of prior biologic therapies (0 vs ≥ 1), and extent of psoriasis ($\geq 3\%$ BSA or $< 3\%$ BSA).

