- b. Subject who does not have evaluation during a specific visit window due to reasons other than COVID-19 infection or logistical restriction related to COVID-19 pandemic will be handled by NRI for that visit. NRI will consider a subject with missing evaluation as a non-responder with the exception for composite binary endpoints including ACR20, ACR50, ACR70, MDA and modified PsARC for which the missing components will be imputed with last observation carry forward to derive composite score before imputing missing evaluations as a non-responder.
- c. Subjects will be considered as non-responders after initiation of rescue medication or initiation of concomitant medications for PsA that could

meaningfully impact efficacy assessment; these medications will be identified prior to database lock and unblinding.

For composite binary endpoints including ACR20, ACR50, ACR70, MDA and modified PsARC, the missing binary values due to COVID-19 infection or logistical restriction will be imputed via MI with the logistic regression option as outlined in [Appendix F](#). For other binary endpoints which are dichotomized from a continuous scale, the MI will be applied to the original continuous scale and the dichotomized endpoint will be derived from the imputed value for missing due to COVID-19 infection or logistical restriction.

Mixed-Effect Model Repeated Measures (MMRM)

The repeated measures analysis will be conducted using a mixed model including observed measurements at all visits. For the MMRM analysis, data collected after initiation of rescue medication or initiation of concomitant medications for PsA use that could meaningfully impact efficacy assessment will be excluded. The mixed model includes the categorical fixed effects of treatment, visit and treatment-by-visit interaction, stratification factors, and the continuous fixed covariate of baseline measurement. An unstructured variance covariance matrix will be used. Parameter estimation is based on the assumption of data being missing at random and using the method of restricted maximum likelihood (REML). The MMRM approach is appropriate in handling missing data due to COVID-19 infection or logistical restriction given the validity of the missing at random assumption. MMRM will be used for the primary estimand of continuous variables (refer to Section 8.4.1).

As Observed (AO)

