8.4 Secondary Efficacy Analyses

8.4.1 Secondary Efficacy Analyses

The secondary endpoints are defined in Section 3.2. Ranked secondary endpoint will be tested in rank order, according to procedures in Section 12.0.

For all binary secondary endpoints, frequencies and percentages will be reported for each treatment group. The primary estimand and analysis method are the same as that for the primary efficacy endpoint as defined in Section 8.3.4. NRI-C missing data handling will be used to analyze the primary estimand (refer to [Appendix D](#)).

For the secondary endpoints applicable only for a sub-population, the estimand will be constructed similarly but based on the sub-population, as defined in the below table.

Endpoint	Sub-population
Psoriasis Area Severity Index (PASI) 90 response at Week 24	Subjects with BSA $\geq 3\%$ at baseline are included in the analysis
Resolution of enthesitis (LEI = 0) at Week 24	Subjects with baseline presence of enthesitis (LEI > 0) are included in the analysis
Resolution of dactylitis (LDI = 0) at Week 24	Subjects with baseline presence of dactylitis (LDI > 0) are included in the analysis

For continuous secondary efficacy variables, primary analysis will be based on the hypothetical estimand. The attributes of the corresponding estimand are outline in [Appendix D](#). The comparison is risankizumab 150 mg vs placebo for patients randomized and treated with at least one dose of study drug. Statistical inference will be conducted using the MMRM model and the associated data handling as described in Section 8.2. The least square (LS) mean and 95% CI for each randomized treatment group and the LS mean treatment difference, the associated 95% CI and the p-value between risankizumab 150 mg group and the placebo group will be provided.

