Appendix E. NRI-C Procedure

Composite Binary Endpoints

Step 1:

Missing binary values are first imputed via MI under MAR assumption using the FCS method with the logistic regression option. The FCS method can handle any arbitrary missing data pattern, without monotone missing requirement. Treatment is included in the FCS imputation model to enable stratified sampling conditional on treatment groups. The imputation model includes gender, race (white vs. non-white), ethnicity, age, baseline BMI, geographic regions, duration of PsA, baseline values of the components of the composite binary endpoint, stratification factors, intercurrent event status, as well as longitudinal response observed at all other visits. The number of imputed datasets is 30 for each PROC MI. Sample codes are as follows:

```
proc mi data=data1 seed=&seed nimpute=30 out=mar_imp;
```

```
class &predcate &postout;  
fcs logistic;  
by treatment;  
var &predcate &predcont &postout;  
run;
```

Note: &predcate (categorical covariates): gender, race (white vs. non-white), ethnicity, geographic regions, concomitant csDMARD at baseline (yes vs no), prior biologic use, extent of psoriasis, and intercurrent event status. &predcont (continuous covariates): age, baseline BMI, duration of PsA, baseline components. &postout: Binary endpoint at week 4, 8, 12, 16, 24

Step 2:

For each imputed dataset, the imputed response status for missing due to reasons other than COVID-19 is overridden by NRI to ensure that multiple imputation is only applied to missing due to COVID-19. Subjects will be considered as non-responders after initiation of rescue medication or initiation of concomitant medications for PsA use that can

meaningfully impact efficacy assessment (including COVID-19 impacted visits of which response status is imputed by MI in step 1).

Step 3:

For each of the 'complete' datasets, the CMH test is performed adjusting for the stratification factors to estimate the treatment difference of risankizumab versus placebo and the corresponding standard error. This is performed with the SAS procedure PROC STDRAE using the Mantel-Haenszel method (Greenland and Rothman 2008, p. 271).⁶

Sample SAS codes are as follows:

```
proc stdrate data=data2 method=mh stat=risk effect=diff;  
population group=TRTP event=N_RESPONDERS total=N_TOTAL;  
strata STRATA / order=data stats effect;  
run;
```

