Note: The input dataset is summary level data including the following variables: treatment group (denoted by TRTP), stratification factors (denoted by STRATA), number of responders per study and treatment group (denoted by N_RESPONDERS) and total number of subjects per study and treatment group (denoted by N_TOTAL).

The results from the 30 'complete' datasets will be synthesized using the SAS procedure PROC MIANALYZE, following Rubin's formula (Rubin, 1987)¹, to derive the MI estimator of the treatment difference for the final statistical inferences. Sample SAS codes are as follows:

```
proc mianalyze data=data3;  
modeleffects RiskDiff;  
stderr StdErr;  
ods output parameterestimates=risk_diff_mh;  
run;
```

Binary Endpoints Dichotomized from Continuous Scale

Step 1:

When a dichotomized variable is derived from a continuous scale, the MI is applied to the original continuous scale. Missing values are imputed via MI with the FCS method.

Treatment is included in the FCS imputation model to enable stratified sampling conditional on treatment groups. The imputation model includes gender, race (white vs. non-white), ethnicity, age, baseline BMI, geographic regions, duration of PsA, baseline value of the endpoint of interest (in continuous scale), stratification factors, intercurrent event status, as well as longitudinal response (in continuous scale) observed at all other visits. The number of imputed datasets is 30 for each PROC MI. Sample codes are as follows:

```
proc mi data=data1 seed=&seed nimpute=30 out=mar_imp;  
class &predcate;  
fcs;  
by treatment;  
var &predcate &predcont &postout;  
run;
```

Note: &predcate (categorical covariates): gender, race (white vs. non-white), ethnicity, geographic regions, current use of csDMARD, prior biologic use, extent of psoriasis, and intercurrent event status. &predcont (continuous covariates): age, baseline BMI, duration of PsA, baseline value. &postout: continuous scale of the binary endpoint at week 4, 8, 12, 16, 24

The dichotomized variable is then derived from the imputed value for each imputed dataset.

Step 2:

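### Resolution of enthesitis and of dactylitis is compared without the baseline LEI or LDI score, so the risk-difference intervals are somewhat wider than they need be

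*SAP*

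**What the plan says.** SAP 8.1 sets the default: "categorical variables will be analyzed using Cochran-Mantel-Haenszel (CMH) test, adjusting for the stratification factors". SAP 2.3 names the factors: "Randomization will be stratified by current use of csDMARD" (none, or at least one), number of prior biologics (none, or at least one) and psoriasis extent (BSA below 3%, or 3% and above). That makes eight strata.

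For binary secondary endpoints, SAP 8.4.1 says "The primary estimand and analysis method are the same as that for the primary efficacy endpoint". Its cross-reference is to 8.3.4 rather than 8.3.3, but both sections use the same CMH. The enthesitis rule is "Subjects with baseline presence of enthesitis (LEI > 0) are included in the analysis", and dactylitis has a parallel rule with LDI. Appendix E Step 3 computes a Mantel-Haenszel risk difference over the strata in each of 30 imputed datasets and pools the results by Rubin's formula. SAP 8.4.2 repeats the same CMH for the as-observed analyses.

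The baseline score appears elsewhere. The Appendix E imputation model for endpoints cut from a scale includes the "baseline value of the endpoint of interest (in continuous scale"). For continuous endpoints, the MMRM in SAP 8.2 adjusts for "stratification factors, and the continuous fixed covariate of baseline measurement", and the ANCOVA in 8.4.2 also includes baseline.

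Protocol Appendix E explains why both endpoints left the ranked list: given the expected subset sizes, "the resulting data are not expected to provide adequate power to be clinically meaningful".

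**The concern.** Response here means reaching a fixed state, zero, from whatever score the subject had at entry. A subject with one tender entheseal site must clear one; a subject with six must clear six. The entry score is therefore likely to be prognostic, and none of the three strata measures entheses or digits. The plan uses the baseline score to impute missing values, then leaves it out of the comparison between arms.

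Precision is at stake. If the score is prognostic, leaving it out widens the interval for the treatment difference. This affects the two endpoints for which the sponsor has already said that information will be short.

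**Working it through.** **1. The plan's own power figures (SAP 2.4).** With 10% dropout, 210 × 0.9 = 189 per arm.
- HAQ-DI: 0.24 / (0.72 × √(2/189)) − 1.96 = 3.24 − 1.96 = 1.28, so power is 90.0% (89.8% by t). This matches the stated figure of approximately 90%.
- ACR20, 35.7% vs 55.7%: 97.6%, consistent with at least 90%.
- No figure is given for enthesitis or dactylitis resolution.

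**2. Subset sizes.** The documents give none for this trial. Protocol 2.1 gives background prevalences, used here only as bounds.
- Enthesitis, 25-51% of 420: 105 to 214 subjects (about 53 to 107 per arm).
- Dactylitis, 8-59% of 420: 34 to 248 subjects.
- Eight strata by two arms is 16 cells, so 105 subjects average 6.6 per cell and 34 average 2.1.

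**3. Unadjusted power in such subsets.** Illustrative rates of 35% vs 55% are assumed, p̄ = 0.45, n per arm:

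power = Φ{[0.20 − 1.96√(2p̄(1−p̄)/n)] / √[(p0(1−p0)+p1(1−p1))/n]}

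For N = 105 (n = 52.5): (0.20 − 1.96 × 0.0971) / 0.0951 = 0.10, giving 54%. The same formula gives 21% at N = 34, 84% at N = 214 and 89% at N = 248. The sponsor's statement about power is therefore plausible when the subsets are small.

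**4. Gain from the baseline score, generic model.** Simulation with 2,500 trials per setting, 1:1 within eight non-prognostic strata, rates 35% vs 55%, and a normally distributed baseline score whose strength is set by its within-arm AUC. If the variance of the risk difference falls by v, the equivalent gain in subjects is v/(1 − v). Power compares the stratified CMH test with the Wald test of treatment in the adjusted logistic model; Monte Carlo error is about 1 point.

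| N | AUC | v | Equivalent extra subjects | Power, CMH → adjusted |
|---|---|---|---|---|
| 105 | 0.6 | 1.6% | 1.6% | 55 → 57% |
| 105 | 0.7 | 12.2% | 13.9% | 55 → 62% |
| 105 | 0.8 | 25.8% | 34.8% | 57 → 69% |
| 126 | 0.6 | 2.0% | 2.0% | 63 → 65% |
| 126 | 0.7 | 10.3% | 11.5% | 61 → 67% |
| 126 | 0.8 | 26.3% | 35.7% | 61 → 74% |
| 214 | 0.6 | 1.9% | 1.9% | 84 → 86% |
| 214 | 0.7 | 9.6% | 10.6% | 85 → 89% |
| 214 | 0.8 | 24.2% | 31.9% | 84 → 92% |
| 248 | 0.6 | 1.0% | 1.0% | 90 → 91% |
| 248 | 0.7 | 10.6% | 11.9% | 89 → 92% |
| 248 | 0.8 | 25.5% | 34.2% | 88 → 96% |

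**5. Gain with an LEI-type count.** Here the odds of reaching zero fall by an assumed factor of 0.74 to 0.55 per extra baseline site. Under assumed LEI distributions this corresponds to an AUC of about 0.63-0.75, so the AUC 0.8 rows above lie beyond it. The estimators compared are the Mantel-Haenszel risk difference and the standardised logistic risk difference.
- 130 per arm, 45% vs 30%: worth 7-17% more subjects; power 72-73% against 73-79%.
- 53 to 130 per arm: worth about 3-20% more subjects. Null rejection is 4.7-6.5% adjusted against 5.7-7.6% for Mantel-Haenszel. Power hardly rises, and can fall slightly when prognosis is weak or the subset is small. Part of this may be that the unadjusted test rejects somewhat too often in sparse strata, which flatters its power.

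**6. Interval width.** A gain of 3-20% multiplies the width by 1/√1.03 = 0.985 to 1/√1.20 = 0.913, so intervals are 1.5-9% narrower. At N = 105 the simulated standard error is about 0.095 and the half-width 1.96 × 0.095 = 18.6 points. That becomes 18.3 to 17.0 points.

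**The case against.** The strongest case for the plan is that nothing in it is wrong. Stratified CMH matches the randomisation and targets the difference in proportions that SAP Appendix D defines. Protocol 7.3 itself names CMH for categorical variables. Both endpoints are unranked, so no confirmatory decision depends on them. Baseline scores are summarised by arm (SAP 7.1), and change from baseline in LEI and LDI is planned with a baseline-adjusted MMRM (SAP 3.3, 8.5). Every input to the size of the gain is assumed. A dactylitis subset near 34 might not support a model with treatment, three factors and a baseline score, and the actual distribution of LDI was not modelled.

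All of this stands, and it limits the point to efficiency. It does not remove the point: the MMRM answers a different question (mean change), and no planned comparison of the resolution proportions themselves uses the baseline score.

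A reader might infer more than the documents support:
- **That MDA has the same problem.** MDA is also compared by CMH, but the power statement covers only enthesitis and dactylitis. MDA is ranked fourth, is analysed in the full FAS and is a 5-of-7 composite with no single baseline score. The BSA stratum already relates to its skin criterion.
- **That the entry score largely decides who responds, or goes unused.** No figure in the documents shows its strength, and it is used for imputation.
- **That chance baseline imbalance biases the result.** Its effect is part of the sampling error that the interval already covers.
- **That adjustment would restore adequate power.** Even at 130 per arm, the best LEI-count case reaches 79%.

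**Conclusion.** The point holds as a modest gain in precision for two unranked endpoints. Resolution of enthesitis and of dactylitis is compared on the randomisation strata alone, while a likely prognostic baseline score, already collected, serves only the imputation.

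Under assumed rates, subset sizes and prognostic strength, adjustment is worth roughly 3-20% more subjects. It is negligible at an AUC near 0.6 and larger only if prognosis is stronger than the LEI-count model assumes. The benefit shows mainly in interval width and should not be presented as a dependable rise in power. For dactylitis the size is less certain than for enthesitis.

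**What to change.** In SAP 8.4.1 and Appendix E Step 3, for these two endpoints only, prespecify before unblinding:
- In each imputed dataset, after the non-responder rules of Step 2, fit a logistic model with treatment, the three stratification factors and baseline LEI or LDI. State the scale on which the score enters.
- Average the predicted probabilities under each arm over all analysed subjects, take the difference with a robust standard error, and pool by Rubin's rules as already planned. The estimand is unchanged.
- Report the result alongside CMH. If it is to replace CMH as the main analysis, align Protocol 7.3 or document the departure.
- State a fallback: CMH alone if the model fails to converge or the subset has fewer than a stated minimum of responders or non-responders. This matters most for dactylitis.

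The cost is SAP wording, standard software and slightly more analysis work; no new data are needed. The drawback is a model-based estimate beside a simpler one. If added after unblinding, it should be labelled post hoc.
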